10.1. Adverse Events

An Adverse Event (AE) is defined as any unfavorable and unintended sign (including an abnormal laboratory finding), symptom, or disease temporally associated with the use of IP, whether or not related to IP. Adverse events will be coded using MedDRA Version 25.1 or higher.

10.1.1. Treatment-Emergent Adverse Event (TEAE)

A TEAE is defined as an AE with onset after the start of IP, or any worsening of a pre-existing medical condition/adverse event with onset after the start of IP and throughout the study. If the date of an adverse event is incomplete and an unambiguous determination could not be made with respect to its onset time versus administration of IP, the adverse event will be assumed to be a TEAE. For imputation of missing AE dates, please refer to Section 7.3.1.

An overview summary table of TEAEs will present the number and percentage of participants as well as the number of events for the following:

- TEAEs
- TEAEs by maximum severity (severe>moderate>mild)
- Study drug-related TEAEs
- Treatment-emergent serious adverse events (SAEs)
- TEAEs leading to interruption of IP
- TEAEs leading to withdrawal of IP
- TEAEs leading to discontinuation from the study
- Treatment-emergent AESIs
- TEAEs leading to death

Incidence of TEAEs in following categories will be provided by SOC and PT. A participant is counted only once under each SOC and PT in case of multiple occurrences of the same AE. These tables will be sorted by overall descending frequency of SOC and then, within a SOC, by overall descending frequency of PT.

- TEAEs
- TEAEs by maximum severity (severe>moderate>mild)
- Study drug-related TEAEs
- Treatment-emergent SAEs
- TEAEs leading to interruption of IP
- TEAEs leading to withdrawal of IP
- TEAEs leading to discontinuation from the study
- TEAEs leading to death

For maximum severity, participants will be counted only once within each SOC and PT at the maximum severity in the following order: severe>moderate>mild; an AE with missing severity will be omitted from

Sponsor: Sage Therapeutics, Inc.; Protocol No.: 547-TRM-201

severity presentation. For relationship to IP, participants will be counted only once within each SOC and PT at the strongest relationship to IP in the following order: related>not related; an AE with relationship missing is treated as related.

All AEs through the end of the study will be listed including, but not limited to, verbatim term, PT, SOC, relationship to study drug, start and end date, seriousness, action taken, and outcome. Separate listings will be provided for SAEs, AEs leading to death, AEs leading to treatment discontinuation, AEs leading to study withdrawal, and AEs leading to dose reduction. TEAEs will be flagged in the listing.

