12.2.6. Recording Adverse Events

Adverse events spontaneously reported by the participant and/or in response to an open question from the study personnel or revealed by observation will be recorded during the study at the investigational site. The AE term should be reported in standard medical terminology when possible. For each AE, the investigator will evaluate and report the onset (date and time), resolution (date and time), intensity, causality, action taken, outcome and seriousness (if applicable), and whether or not it caused the participant to discontinue the IP or withdraw early from the study.

Intensity will be assessed according to the following scale:

- Mild: symptom(s) barely noticeable to participant or does not make participant uncomfortable; does not influence performance or functioning; prescription drug not ordinarily needed for relief of symptom(s)
- Moderate: symptom(s) of a sufficient severity to make participant uncomfortable; performance of daily activity is influenced; participant is able to continue in study; treatment for symptom(s) may be needed
- Severe: symptom(s) cause severe discomfort; symptoms cause incapacitation or significant impact on participant's daily life; severity may cause cessation of treatment with IP; treatment for symptom(s) may be given and/or participant hospitalized

It is important to distinguish between serious and severe AEs. Severity is a measure of intensity whereas seriousness is defined by the criteria under Section 12.2.2. An AE of severe intensity may not necessarily be considered serious.

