13.6.1. Adverse Events

Adverse events will be coded using Medical Dictionary for Regulatory Activities (MedDRA) Version 25.0 or higher. A treatment-emergent adverse event (TEAE) is defined as an AE with onset or worsening of severity after the first dose of brexanolone.

The proportion of participants experiencing TEAEs will be displayed by treatment group and by system organ class and preferred term. Summaries will be provided by severity (mild, moderate, severe) and by causality (related, not related to IP). TEAEs leading to discontinuation or interruption of treatment or withdrawal from the study and any treatment-emergent SAEs will be summarized. All AEs and SAEs through the end of the study will be listed.

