4.6. Study Procedures and Flowchart

The study design is summarized in the flow chart below. Reference Protocol Schedule of Assessments (Tables 2 and 3) for the complete Schedule of Activities.

Figure 1. Study Design

Screening Day -28 to		Treatment Period Day 1	Follow-up Pe Day 2 to Da	
Clinic Assessments Day -28 to Day -8	Remote Assessments Day -7 to Day -1			
	Daily Remote Assessment Reminder Day -7 to Day -1		Daily Remote Assessment Reminder Day 2 to Day 6	
		Clinic Treatment Visit Day 1	Safety Phone Call Day 4	End Stud Visi Day

5. **Endpoints**

5.1. **Primary Endpoint**

Incidence of treatment-emergent adverse events (TEAEs)

5.2. **Secondary Endpoints**

- Change from baseline to Hour 6 of infusion in VAS-L ratings
- Change from baseline to Hour 6 of infusion in VAS-A ratings
- Change from baseline to post-infusion in VAS-L ratings measured via daily diary over multiple
- Change from baseline to post-infusion in VAS-A ratings measured via daily diary over multiple

•	•	Change from baseline in vital signs, electrocardiogram (ECG), and clinical laboratory parameters

Sponsor: Sage Therapeutics, Inc.; Protocol No.: 547-TRM-201

6. Analysis Sets

Details on the process for defining analysis datasets are located in the Data Review and Definition of Analysis Sets SOP (3911).

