7.3.1. Adverse Events (AE)

If an AE start date is completely missing, do not impute the date but consider it as a TEAE, unless the AE end date is before the initiation of treatment, in which case the AE will be considered prior.

For partial AE start dates:

- When the year is known but the month and day is unknown, then:
 - If the year matches the year of first dose and the end date (if present) is after first dose date, or AE is ongoing, then impute as the month and day of earlier date of (the first dose date + 1 day, last dose date).

Sponsor: Sage Therapeutics, Inc.; Protocol No.: 547-TRM-201

- If the year of AE onset < year of initiation of the treatment, then the month and day will be set to December 31st.
- If the year of AE onset > the year of initiation of treatment, then the month and day will be set to January 1st.
- If the year and month are known, but the day is unknown, then:
 - o If the year of AE onset = the year of initiation of the treatment and:
 - The month of AE onset = the month of initiation of the treatment, then the day will be set to the day of initiation of the treatment.
 - The month of AE onset < the month of initiation of the treatment, then the day will be set to the last day of month of the particular year.
 - If the month of AE onset > the month of initiation of the treatment, then the day will be set to the 1st day of month.
 - o If the year of AE onset < the year of initiation of the treatment, then the day will be set to the last day of month of the particular year.
 - o If the year of AE onset > the year of initiation of the treatment, then the day will be set to the 1st day of month.
- If the imputed AE onset date is after the AE stop date, then the onset date will be set to the stop date.
 - When the year and day are present and the month is missing, treat it as if the day is missing, and only year is present. Follow the imputation rules for "year is known, but the month and day is unknown."
 - When the year is missing, but the month and/or day is known, treat this date as missing; do not impute.
- 7.3.2. Dates in Disease History (Dates of diagnosis, current episode, first episode)
 - If the year is present and the month and day are missing, then the month and day will be set to January 1.
 - If the year and day are present and the month is missing, then the month will be set to January.
 - If the year and month are present and the day is missing, then the day will be set to the 1st day of month.

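### SAP 10.1.1 leaves ungraded TEAEs out of the maximum-severity tables, so the severe and moderate-or-worse counts can be too low but never too high; a missing-severity row would fix this

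*SAP*

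**What the plan says.** SAP 10.1.1 sets the counting rule for severity: "participants will be counted only once within each SOC and PT at the maximum severity", with severe ranked above moderate and moderate above mild. For an event without a grade it adds that "an AE with missing severity will be omitted from" the severity presentation.

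Other gaps in AE data are resolved differently:

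- **Relationship (SAP 10.1.1, same paragraph):** "an AE with relationship missing is treated as related".
- **Start date (SAP 7.3.1):** "If an AE start date is completely missing, do not impute the date but consider it as a TEAE", except where the end date falls before treatment. SAP 10.1.1 also counts an event as a TEAE when an incomplete date leaves its onset unclear.

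The overview table in SAP 10.1.1 carries a row for all TEAEs and rows by maximum severity, and both also appear by SOC and PT. The SAP text describes no category for a missing grade. Severity is not among the fields named for the AE listing, although that list is open-ended. Table shells are held in separate documents (SAP section 15).

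Protocol 12.2.6 asks that, for every AE, "the investigator will evaluate and report the onset (date and time), resolution (date and time), intensity, causality" and other attributes. Protocol 13.6.1 plans TEAE summaries by severity and by causality, but gives no rule for a missing grade. The primary endpoint is the incidence of TEAEs (SAP 5.1). SAP section 12 expects about 10 participants to be dosed instead of 24.

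**The concern.** Omitting an ungraded event can work in two ways. If it is the participant's only TEAE in that SOC or PT, the participant leaves the severity table at that level. If there are graded events as well, the participant is shown at the highest recorded grade, which may be lower than the true maximum. Neither route can move anyone to a higher grade.

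The primary objective is safety and tolerability, and the severity breakdown is one of the summaries a reader will use to judge tolerability. A counting rule whose only possible error makes the drug look milder is a poor choice, and the SAP gives no reason for it. Missing dates and missing relationship are both resolved towards counting the event. The relationship rule only shows the inconsistency; the omission alone causes any understatement.

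**Working it through.** **Inputs.** The counting and omission rules come from SAP 10.1.1, and the number dosed (about 10, against 24) from SAP section 12. The share of TEAEs with a missing grade is not given, so only the direction of the effect and the weight of one participant can be computed. No figure in the plan depends on the rule, so there is none to reproduce.

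**Direction.** Take one participant with k TEAEs in one PT, with grades coded 1 (mild) to 3 (severe). The true maximum M is the maximum over all k grades. The SAP maximum O is the maximum over the recorded grades only, and is empty if none is recorded. O is taken over a subset, so O can never exceed M.

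For k = 1 to 3, every pattern with at least one missing grade was enumerated:

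- Number of patterns: sum of 3^k × (2^k − 1) = 3×1 + 9×3 + 27×7 = 3 + 27 + 189 = 219.
- Maximum raised: 0.
- Maximum unchanged: 120.
- Maximum lowered: 60.
- Participant removed because all grades are missing: 3 + 9 + 27 = 39.
- Check: 0 + 120 + 60 + 39 = 219.

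The severe, moderate-or-worse and any-graded counts were never raised. The separate mild row gained a participant in 34 patterns and the moderate row in 26 (34 + 26 = 60, the lowered patterns). These are counts of patterns, not probabilities.

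**Weight of one participant.** 1/10 = 10.0 percentage points; 1/24 = 4.2 points.

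**Illustration (assumed counts).** Ten are dosed and six have a TEAE: three mild, one moderate, one severe, and one whose only TEAE is ungraded.

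| Row | SAP rule | With a missing row | Missing counted as severe |
|---|---|---|---|
| Mild | 3/10 | 3/10 | 3/10 |
| Moderate | 1/10 | 1/10 | 1/10 |
| Severe | 1/10 (10%) | 1/10 (10%) | 2/10 (20%) |
| Severity missing | none | 1/10 (10%) | none |
| Sum of rows | 5/10 (50%) | 6/10 (60%) | 6/10 (60%) |
| All TEAEs | 6/10 (60%) | 6/10 (60%) | 6/10 (60%) |

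If one of the three mild participants also had an ungraded event, the SAP column would not change and nothing would show. With the missing row, the table would read 2/10 mild and 2/10 missing.

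**Check of the fix on the same patterns.** A recorded severe event settles the maximum whatever the missing grade is. That holds in 6 patterns with two events (2 positions × 3 possible missing grades). With three events it holds in 45 patterns with one grade missing (3 positions × 5 recorded pairs containing a severe × 3) and in 27 with two missing (3 positions × 9). The total is 6 + 45 + 27 = 78, and these stay correctly in the severe row. The other 219 − 78 = 141 go to the missing row, so no one is shown at a grade that may be too low. The true severe count then lies between the severe row and the severe row plus the missing row.

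**The case against.** The strongest points on the other side:

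- **The trigger should be rare.** Protocol 12.2.6 requires intensity for each AE. Protocol 14.1 has monitors check the eCRF against source. There are one or two sites, one supervised infusion and about a week of follow-up. This stands, and it limits the practical impact.
- **The most important events do not depend on a grade.** SAEs, AESIs, deaths, and TEAEs leading to interruption, withdrawal of treatment or study discontinuation are summarised separately. This also stands.
- **The omission is partly visible.** A participant removed altogether shows as a shortfall against the all-TEAEs row, and the shells may already carry a missing row. This stands only in part. A down-graded maximum leaves no shortfall, and the listing text does not commit to showing severity.
- **The plan says missing data are not imputed (SAP 7.3).** The SAP already departs from this for AE dates and relationship, and a missing row imputes nothing.

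Three stronger readings are tempting, and the documents do not support them. A reader might infer that the primary endpoint is understated. It is not: an ungraded TEAE still counts in the overall and SOC/PT incidence tables. A reader might infer that every severity row can only fall. The mild and moderate rows can rise, because a participant with a worse ungraded event is shown at a lower grade. And a reader might infer from the relationship rule that an ungraded event should be counted as severe in the main table. That would assert, without any observation, the severe discomfort or incapacitation by which Protocol 12.2.6 defines that grade. It would replace a one-sided error with the opposite one. Treating a two-level attribute as worst case does not oblige the same for a three-level grade.

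**Conclusion.** The point holds for the severity breakdown only. Under the stated rule, the counts of severe, moderate-or-worse and any-graded TEAEs can be understated and cannot be overstated. Each participant affected is worth 10 percentage points at about 10 dosed, or 4.2 points at 24. The primary endpoint is unaffected. The effect is zero if no grade is missing at database lock, and the documents give no basis for estimating how often one will be. The conclusion assumes that the tables follow the SAP text; the shells were not available. This is a low-cost improvement to the reporting rule and does not threaten the study's main conclusion.

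**What to change.** Before database lock, replace the omission rule in SAP 10.1.1:

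1. Add a *Severity missing* row to the overview and to the SOC/PT maximum-severity tables. At each level, place there any participant who has an ungraded TEAE and no recorded severe TEAE. Participants with a recorded severe TEAE stay in the severe row. The rows then add to the TEAE total.
2. Where events are counted as well as participants, count each ungraded event in the missing row.
3. Name severity among the fields of the AE listing.
4. Optionally, footnote a worst-case count (severe plus missing). Keep it out of the main rows so that no participant appears twice.

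The cost is one changed sentence, one extra row in two tables and one listing field. If grades are missing, slightly fewer participants will be shown as mild or moderate. If none is missing, the new row is zero and the tables do not change.

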10.1.2. Adverse Event of Special Interest (AESI)

An AESI is an AE/SAE of scientific and/or medical concern, specific to the product or program for which ongoing monitoring and rapid communication by the investigator to the sponsor is required. The following events are considered AESIs and collected as an AESI:

- Excessive sedation
- Loss of consciousness
- Any sedation-related AE that leads to dose reduction, interruption, or termination

Treatment-emergent AESIs will be summarized. All AESIs (including those with onset or worsening before the start of IP) will be separately listed, in addition to being included in the primary TEAE tables discussed above. Excessive sedation and loss of consciousness will be reported in a listing for the information including the timepoint, whether the participant was assessed for excessive sedation, and the date and time.

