13.6. Safety Analyses

The primary endpoint of this study is the incidence of TEAEs. This will be primarily assessed with TEAE tables presenting per-participant frequency counts and percentages within each unique combination of System Organ Class and Preferred Term. Please see Section 13.6.1 for additional detail.

Generally, safety and tolerability of brexanolone will be evaluated by incidence of TEAEs and SAEs, as well as changes from baseline in vital signs measurements, ECGs, and clinical laboratory parameters,

Safety data will be listed by participant and summarized by treatment group. All safety summaries will be performed on the Safety Set using treatment received.

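### Read literally, SAP 10.1.2 puts AESIs from before the infusion into the primary TEAE tables; this conflicts with the TEAE definition and could inflate those tables, though the case is unlikely to arise

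*SAP*

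**What the plan says.** The primary endpoint is a count of treatment-emergent events. Protocol 13.6 states: "The primary endpoint of this study is the incidence of TEAEs". The display is to be "TEAE tables presenting per-participant frequency counts and percentages within each unique combination of System Organ Class and Preferred Term".

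The definition is consistent across the documents. SAP 10.1.1 reads "A TEAE is defined as an AE with onset after the start of IP, or any worsening of a pre-existing medical condition/adverse event", where the worsening must also follow the start of the investigational product (IP). Protocol 12.2.1 says the same, and protocol 13.6.1 has "an AE with onset or worsening of severity after the first dose of brexanolone".

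SAP 10.1.2 names three kinds of AESI: excessive sedation, loss of consciousness, and a sedation-related event that changes or ends dosing. It then gives two reporting rules in succession. The first is "Treatment-emergent AESIs will be summarized". The second begins "All AESIs (including those with onset or worsening before the start of IP) will be separately listed, in addition to being included" and gives the destination: "in addition to being included in the primary TEAE tables discussed above".

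**The concern.** In the second rule the only grammatical subject is the full set of AESIs, and the parenthesis extends that set to events from before the infusion. The same subject governs both the listing and the inclusion in the TEAE tables. A programmer working from this sentence would place a pre-infusion AESI in a table whose definition excludes it.

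The tables concerned carry the primary endpoint, and loss of consciousness and excessive sedation are terms that the protocol singles out for rapid reporting (12.2.3). With so few participants, one event counted wrongly would show in the table, and the error can only raise the count.

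**Working it through.** **1. The statements side by side**

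| Place | Which events it covers |
|---|---|
| SAP 10.1.1, definition | Only events that begin or worsen once IP has started |
| Protocol 12.2.1 and 13.6.1 | The same |
| SAP 7.3.1, missing start date | An event that ended before treatment is treated as prior, not as a TEAE |
| SAP 10.1.1, overview table | The AESI row is limited to treatment-emergent AESIs |
| SAP 10.1.2, first rule | Treatment-emergent AESIs only |
| SAP 10.1.2, second rule | All AESIs, pre-infusion ones expressly included, sent to the listing and to the TEAE tables |

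The last row disagrees with the other five. No text says which prevails.

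**2. Can the case arise?**

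- Adverse events are reported from consent (protocol 12.2.1), and Screening lasts up to 28 days (protocol 7.1). The parenthesis in SAP 10.1.2 itself provides for AESIs before IP.
- Exclusion criterion 1 covers unexplained loss of consciousness. A faint with a clear cause, such as one at a blood draw, is not plainly covered.
- CNS depressants must be stopped at least 14 days or 5 half-lives before IP, whichever is longer (inclusion criterion 7). Some participants may therefore still be taking them early in Screening.
- Against this, the third AESI category presupposes a running infusion. A participant who is never dosed is outside the Safety Set (SAP 6.4) and so outside the tables.

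The case is possible but unlikely.

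**3. Inputs for size**

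The disputed sentence states no figure, so there is none to reproduce for it. The denominator is the number dosed: about 10 (SAP 12) or up to 24 (protocol 7.2, SAP 4.3). The planned 24 fits its stated basis: 24 × (1 − 0.20) = 19.2, or approximately 20 completers.

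**4. Effect on a preferred-term row**

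A participant counts once per system organ class and preferred term (SAP 10.1.1). One dosed participant with a pre-infusion AESI and no TEAE under that term adds 1/N:

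- N = 10: 1/10 = 10.0 percentage points
- N = 24: 1/24 = 4.2 percentage points

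If the participant also has a true TEAE under the same term, the row does not change. If the earlier event worsens after IP starts, it is properly a TEAE and there is no error.

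**5. Effect on the any-TEAE row**

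This row rises only if the participant has no true TEAE at all. Let p be the probability of at least one true TEAE. The documents give no value, so I assume a range of 30% to 90%. I also assume that p is unrelated to having had a pre-infusion AESI. The expected rise per affected participant is (1 − p)/N:

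- N = 10: 0.7/10 = 7.0 points at p = 30%; 0.1/10 = 1.0 point at p = 90%
- N = 24: 0.7/24 = 2.9 points at p = 30%; 0.1/24 = 0.4 points at p = 90%

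With no affected participant, both effects are zero.

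**The case against.** The best reply is that context settles the meaning. Every table listed in SAP 10.1.1 is confined to TEAEs or treatment-emergent events. The rule immediately before the disputed one is confined in the same way. SAP 10.1.2 neither redefines a TEAE nor creates a row for pre-dose events. On this reading the parenthesis belongs to the listing, and the rest only confirms that AESIs are not taken out of the TEAE tables where they qualify. The SAP also lists every adverse event with start and end dates and flags TEAEs in that listing, so a misplaced event could be seen.

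Much of this stands. It makes a drafting slip the likeliest explanation. It does not remove the conflict, because a specific sentence and a general definition give different instructions and the SAP does not rank them. The listing flag would reveal a wrong count but would not correct the table.

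Two stronger readings are tempting, and the documents support neither:

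- A reader might infer that the plan does inflate the primary endpoint. It does so only if a participant has an AESI between consent and infusion, is still dosed, has no TEAE under the same term, and the sentence is programmed literally.
- A reader might infer that a pre-dose event would be attributed to brexanolone. TEAE status is not attribution. The investigator assesses relationship for each event, and lack of a temporal relationship points to not related (protocol 12.2.5). Drug-related TEAEs have their own tables. Only an event with a missing relationship is treated as related (SAP 10.1.1), and the protocol requires that assessment for every event.

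**Conclusion.** The point holds as an internal contradiction in a counting rule for the primary endpoint tables, most probably a slip in wording. Its consequence is conditional: 10 percentage points in one preferred-term row per affected participant at about 10 dosed, 4.2 at 24, and a smaller expected change in the any-TEAE row under the assumed range for p. The probability of an affected participant is low. The documents give no rate, so I put no figure on it. Sample size and error rates are unaffected; the safety analysis is descriptive. This is a minor correction, worth making because of which tables it touches and how few participants they describe.

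**What to change.** Replace the two reporting sentences on AESIs in SAP 10.1.2 with wording such as:

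> Treatment-emergent AESIs are included in the TEAE tables. All AESIs, including those with onset before the start of IP, are listed separately, with a treatment-emergent flag.

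Keep the existing AESI row in the overview table. The flag is already planned for the adverse event listing, so the change extends it to the AESI listing. No information on pre-infusion events is lost, because they remain in the listing.

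The cost is a short edit to one SAP paragraph and a check that the table and listing shells agree. No new data are needed, and I see no downside. It should be settled before database lock, the point by which protocol 13 requires the SAP to be final.
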